occur on different dates. The following research procedures will be completed prior to the PI's determination of subject's study eligibility:1. Obtain Informed Consent, assignment of subject unique identifier2. Performance of history and physical exam inclusive of participant's limb with evaluation for heterotopic ossification (HO); exam completed by PI and / or a co-investigator. 3. The investigator will rate the appearance of the graft site using a limb volume and appearance grading scale4. Collection of subject's vital signs (Temperature, heart rate (HR), respiratory rate, blood pressure (BP), medication profile to include prescription and vitamins / supplements, allergies, height, weight, Body mass index (BMI) calculation, collection of demographic information to include date of birth, gender, race, hand dominance, ethnicity, level of education, relationship status, smoking status and employment status. 5. All participants who are women of child bearing potential will receive a urine pregnancy dip test. If the test result is positive the subject will not continue participation in this research study. 6. Structured Clinical Interview for DSM-IV (SCID; DSM is the diagnostic and statistical manual of mental disorders) will be included in the baseline to evaluate the presence/absence of Axis I psychiatric disorders. This evaluation will be completed using a standard psychiatric diagnostic interview that enables determination of DSM-IV-based diagnoses. As part of the clinical interview a demographic history will be completed. The information contained in the SCID will be collected by a member of [name] clinical team who is experienced in psychosocial interviewing with participants. This SCID will take approximately 45-60 minutes of the subject's time to complete. Individuals who manifest either: 1) evidence of currently active alcohol or psychoactive drug abuse or dependence on the SCID interview, or 2) a GAF score of 40 or lower due to any acute psychiatric symptomatology (e.g. suicidality, psychosis, severe depression or mania) will be reviewed by the Co-I for Psychosocial Assessment with the PI for determination of possible medical instability. Final determination of medically unstable status will be made by the PI on the basis of overall medical status and appropriateness for medical procedures; the patient may be considered ineligible for study participation per the Physician's discretion. 7. Medical and surgical history review: If the subject has been followed at UPMC facilities, the principal investigator, co-investigators and / or study staff will perform a medical history review (pertaining to the trauma event and surrounding surgical and medical procedures). A medical history review will consist of prior procedures to include, but not be limited to blood tests (including but not limited to complete blood count (CBC) with Differential and Platelets, comprehensive chemistry panel, urinalysis, and culture results) operative procedures, physical therapy assessments, consultations, history of Heterotopic Ossification(HO), CT, MRI scans, EKG, Chest X-rays, history and physical exams. If medical records do not accompany the subject or are not available at the time of screening evaluation for investigator review, the investigator in lieu of direct medical record review will accept direct report from the referring physician, prosthetics and/or orthotics referral source and /or subject self report and will document this reported information to research chart. This report will consist of past medical /surgical history pertaining to the affected limb injury and/or events surrounding the limb trauma. The Principal Investigator will base determination of study eligibility on a combination of

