
evaluation criteria to include physical examination, screening lab values, referral physician direct report, prosthetics and/or orthotics referral direct reports and /or subject self report, study O&P evaluation and psychological (SCID) assessment all pertaining to past injury and current status of the area of interest. 8. Baseline evaluation of amputation stump pain, the study coordinator will provide a Pain Assessment form to the participant to complete. This form will document the nature/character of the discomfort limiting function and or interferes with their ability to use a prosthetic device. The subject will be instructed to document the discomfort to include frequency, location, intensity (1 to 10 scale with 10 as most intense), type of pain (physiological or phantom). It will include subject self-intervention related to pain and use of prosthetic devices9. Blood Tests- approximately 30mls (2 tablespoons) will be collected for the following laboratory assessments: Serum CBC with Differential and platelets .Comprehensive Chemistry panel including Calcium, Pre-Albumin, and Albumin'PT/ PTT/ INR On receiving the laboratory results, the Investigator will initial and date the results and assign clinical significance to any out of range values. Subjects with clinically significant results attributed to any disease entity will be evaluated and per MD discretion excluded from the trial.10. Orthotics and Prosthetics: One of the aims of this study is to evaluate prosthetic fit problems at an amputation site that limits function and / or interferes with the ability to use a prosthesis which is known to have a direct impact on the ability to perform activities of daily living as well as social participation. This aim is important to identify pain and functional issues associated with the use of a prosthesis and/or other assistive technology used in conjunction with a prosthesis or in lieu of. This study will seek to address residual limb problems for individuals with upper and lower limb loss, including individuals with partial hand, partial foot and more proximal injuries. We will utilize this novel procedure to help improve function and tolerability for individual with limb loss. Reasons for "intolerability" may include inappropriate soft tissue padding, soft tissue coverage, or pain that doesn't allow the consistent wearing of a prosthetic socket. This may be manifested by excessive pain, inability to achieve adequate suspension of the prosthesis on the individual, continual skin breakdown, excessive pressure/shear on skin, soft tissue, nerves, scars, etc. The degree of pain and intolerability associated with the prosthesis can be described as follows; While a generally accepted score of 4 or greater on a visual analogue scale from zero (no pain) to ten (worst possible pain) is considered intolerable, currently, the field of amputee and prosthetic care lacks a validated instrument to measure "intolerability" of socket fit or prosthetic use. Therefore, we will consider individuals for this procedure, who by the patient and rehabilitation teams' report are unable to successfully progress in prosthetic rehabilitation despite multiple interventions, including surgical and non surgical. These patients will have undergone multiples prosthetic limb and socket adjustments, various external padding attempts and even often interventions such as skin grafts, muscle flaps, neuroma injection or resection, or heterotopic ossification surgical resection. We will only consider patients who have received a minimum of 3 months of unsuccessful prosthetic fitting trials for inclusion in this study. This information pertaining to the history of prosthetic fit attempts may be received from referral physician, prosthetics and/or

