
recordings. 3.) All participants who are women of child bearing potential will receive a urine pregnancy dip test. If the test result is positive the subject will not continue participation in this research study. 4.) Collection and review of new medications to include prescription and vitamins / supplements, allergies and vital signs (Temp, HR, Resp, BP), weight, body mass index (BMI) calculation, and adverse event reporting. 5.) Serial Computed Tomography Imaging or MRI scan will be performed. A high resolution Computed Tomography (CT) Scan of the amputation stump will be performed at Presbyterian Hospital and will take approximately 60 minutes. This scan will be pre-procedural and will serve as a baseline. All CT scans will be performed on a 64-slice scanner (LightSpeed, GE Healthcare), using slice thickness of 1.25 mm and pitch of 1.375. kVp, mA, and FOV will be optimized to the subject and body part to be imaged. Soft tissue and bone kernels will be employed. These images will be volumetrically reformatted into coronal and sagittal planes for confirmation of findings. Additionally, surface-rendered volumetric reformats will be created emphasizing both bony structures and soft tissues. In the event that a CT scan is contraindicated or declined by a study participant, MRI will be performed using a 1.5 T MRI scanner (Signa HDx, GE Healthcare). The MR imaging protocols will include coronal and axial planes using T1-weighted spin echo sequences as well as coronal, axial, and sagittal planes using T2-weighted fast spin echo with fat suppression and/or short tau inversion recovery (STIR) sequences. Again, FOV, TR/TE time, acquisition time and other parameters will be optimized to the subject and body part to be imaged. Intravenous contrast will not be administered for either CT or MR imaging. Images will be reviewed by radiology. Volume measurements of the implanted material will be made on all post-procedural CTs or MRIs. These volumetric measurements are expected to be precise to within 5% of the actual volume of material. Trends in volume of tissue will be analyzed over time across the multiple CT or MRI scans. Both linear and volumetric measurements will be used to quantify implanted material. Subjects must remove compression sleeves prior to CT scans. 6.) To further evaluate pre-surgical amputation stump pain, the study coordinator will provide a Pain Assessment form to the participant to complete. This form will document the nature/charter of the discomfort limiting function and or interferes with their ability to use a prosthetic device. The subject will be instructed to document the discomfort to include frequency, location, intensity (1 to 10 scale with 10 as most intense), type of pain (physiological or phantom). It will include self interventions related to pain and use of prosthetic devices. 7.) Psychosocial Assessment: One of the aims of the proposed study is to evaluate pre- and post-operative quality of life and symptoms of psychological distress. This aim will also consider psychosocial factors (pre- and post- surgery) that predict psychological well-being and quality of life outcomes following surgery. The aim is important for identification of psychosocial factors that may play a role in and be critical to enhancing quality of life outcomes from amputation stump surgery. Participants will be asked to complete a psychosocial battery that includes: a) self-report measures of satisfaction with physical appearance, anxiety and depressive symptoms, social functioning and social avoidance and distress and; b) questionnaires that assess significant predictors of quality of life

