
outcomes from post-trauma limb surgery: perceived social support, self-esteem, coping style and pre-surgical expectations of/post-surgical outcomes. A research technician experienced in psychosocial interviewing with participants will meet with each participant during the baseline evaluation to administer the self-report battery of psychosocial questionnaires. A comprehensive battery of tests for evaluation of quality of life has been assembled for this study. It is important to properly determine the impact of the surgical changes and the investigators have selected psychosocial assessment instruments to evaluate four domains:a. Satisfaction with appearance/surgical outcomes – The Satisfaction with Appearance (SWAP) scale (145) is a 14-item questionnaire with good internal consistency and test-retest reliability that measures both subjective and social-behavioral aspects of body image and has been used in populations with significant physical disfigurements or deformities. b. Satisfaction with Medical/Health Services - Patient Satisfaction with Health Services – the Client Satisfaction Questionnaire (CSQ-8) is a widely used brief inventory of satisfaction with services (amount of help, kind of help, availability of help) provided by a medical service or program (146). c. Social Functioning, Distress, Depression and Avoidance - To evaluate hypothesized pre- versus post-operative changes in quality of life, social functioning, symptomatology and coping, we will include the following measures: • Social Distress and Avoidance - Individuals with disfigurements can suffer extreme anxiety and avoidance in interpersonal interactions. The Social Anxiety and Distress (SAD) Scale (147) is a widely used measure of social avoidance and distress that has shown to be sensitive to pre-/post- surgical improvement in recent studies of patients undergoing reconstructive surgery for significant physical deformity. • Anxiety and Depressive Symptomatology will be monitored using the Beck Depression Inventory, PHQ brief and the PCL-S (Post trauma checklist- Brief) (148), a self-report questionnaire that taps post traumatic stress disorder (PTSD) symptoms for use among individuals in the military. • Self-esteem will be assessed by the Rosenberg Self Esteem Inventory (149), a brief (10-item), a self-report inventory examines how social structural positions relate to self-esteem. • Coping Style will be assessed with the Brief COPE inventory (150) an abbreviated version of the situation-specific coping inventory (151) that has been effectively used to characterize psychological coping with physical illness and disability. An extensive body of research on clinical and psychosocial outcomes from surgical and medical interventions has yielded evidence that psychosocial coping style is an important factor that contributes to psychological well-being, physical health and quality of life outcomes. • Perceived Social Support will be analyzed by the Perceived Social Support Questionnaires(PSSQ)-Family and Friends (152). This 6-item self-report inventory with satisfactory internal reliability and construct validity that inquires regarding the perceived availability of social support for needs for support, information and feedback. Social support, along with psychosocial coping cognitions and behaviors contributes significantly to psychological well-being, physical health and quality of life outcomes. Each of these may be important covariates that contribute to variance in quality of life outcomes in this study.d. Quality of Life and General Functioning Outcomes - Quality of life and general functional status will be evaluated using the SF-36 (153, 154), a self-report inventory

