Pain and Serial computed tomography imaging will be performed and measured as parametric data sets before fat grafting and afterwards at various time points using a paired t-test model. Repeated measures analysis of variance will be used to evaluate change over time in all outcome measures. Using standard conventions of alpha=0.05 and beta=0.8, an enrollment of thirty patients may provide sufficient power to detect a Cohen's effect size of about 0.9 which is anticipated to be adequate for detecting clinically meaningful differences in the volume of soft tissue. A composite functional score will be constructed from the prosthetics and occupational therapy evaluations and compared between study groups. The details of this analysis, including which evaluations will be included in the score and relative weight, can be best determined as the study progresses and initial data sets are acquired. Additionally, each assessment score from the specific tests will also be considered individually for comparison.

[reviewer notes-]

Section 2 - Research Design and Methods

2.19

Will this research be conducted in (a) a foreign country and/or (b) at a site (e.g., Navajo Nation) where the cultural background of the subject population differs substantially from that of Pittsburgh and its surrounding communities?* No

Note that copies of training records, licenses, certificates should be maintained in the study regulatory binder and are subject to audit by the Research Conduct and Compliance Office (RCCO).

Section: Section 2 - Research Design and Methods

In addition, individuals planning to conduct human subject research outside the United States must complete an optional module on the CITI training website: International Studies. Click [here](#) to access the instruction sheet for accessing optional CITI modules.

- 2.19.1 Address the following for each of the foreign/culturally different sites where this research will be conducted:
- Name of site
 - Name of authorized individual (e.g., IRB Chair) from the local IRB or other human subject protections entity that is responsible for the review and approval of the project; upload approval letter with an English translation, if applicable
 - Name and qualifications of the site collaborator responsible for the conduct of the research (e.g., site PI)
 - The anticipated number of subjects that will be enrolled at that site
 - If Federally funded, provide the Federalwide Assurance number (FWA) assigned to the site *

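### Pain is rated twice before surgery, but section 2.18 states no baseline adjustment between arms and does not say which rating is the before value

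*Combined protocol and SAP*

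**What the plan says.** Pain is rated on one form, with intensity from 1 to 10, at two points before surgery.

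- **Screening (2.5.1, item 8):** "Baseline evaluation of amputation stump pain, the study coordinator will provide a Pain Assessment form to the participant to complete". The list containing this item opens with "The following research procedures will be completed prior to the PI's determination of subject's study eligibility".
- **Pre-graft visit (2.6, item 6):** "To further evaluate pre-surgical amputation stump pain, the study coordinator will provide a Pain Assessment form to the participant to complete".

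Section 2.17 lists improvement of pain among the primary outcomes, to be compared between standard grafting (n=15) and cell-enriched grafting (n=15). Section 2.18 says that pain and imaging are "measured as parametric data sets before fat grafting and afterwards at various time points using a paired t-test model", and then: "Repeated measures analysis of variance will be used to evaluate change over time in all outcome measures". It does not name the pre-operative pain value, list the time points that enter the ANOVA, or mention a baseline covariate.

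The word baseline is not tied to one visit. For pain it heads the screening rating. For imaging it means the pre-graft CT ("This scan will be pre-procedural and will serve as a baseline"), and the psychosocial battery, also given at the pre-graft visit, is placed "during the baseline evaluation to administer the self-report battery of psychosocial questionnaires".

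**The concern.** There are two matters, and they bear on different comparisons.

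**Between arms.** With 15 patients per arm, precision is scarce. Pre-operative pain is likely to predict post-operative pain, and it is already being collected. An analysis that leaves it out, or uses it only through a change, gives up precision that costs nothing to keep.

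**Within groups.** Patients enter because pain limits use of a prosthesis or assistive device (section 3.13). The rating headed as baseline is completed before eligibility is decided. A rating available at selection tends to fall on re-measurement even when nothing has changed. Both arms receive a graft and there is no untreated arm, so the objective that fat grafting itself relieves pain (section 1.1) can be addressed only by the before/after test. That is the test in which such a fall would look like relief.

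**Working it through.** **The plan's own figure.** Section 2.18 gives a detectable effect of about 0.9 SD with 30 patients, for soft-tissue volume and not for pain. For two unadjusted means, the detectable d is (z for alpha + z for power) × √(2/15).
- One-sided 0.05: (1.645 + 0.842) × 0.365 = 0.91, which reproduces the figure.
- Two-sided 0.05: (1.960 + 0.842) × 0.365 = 1.02, which does not.

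The section does not state sidedness. The two-sided value is used below.

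**Inputs that the documents do not give.** No pain SD, no baseline-outcome correlation (ρ) and no test-retest correlation (r) is stated. All three are assumptions here.

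**Between-arm variance, relative to an unadjusted comparison of post-operative means:**

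| ρ | Unadjusted | Change score, 2(1−ρ) | ANCOVA on one rating, 1−ρ² |
|---|---|---|---|
| 0.3 | 1.00 | 1.40 | 0.91 |
| 0.5 | 1.00 | 1.00 | 0.75 |
| 0.7 | 1.00 | 0.60 | 0.51 |
| 0.8 | 1.00 | 0.40 | 0.36 |

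ANCOVA is lowest in every row. At ρ = 0.5 it is 25% below both alternatives, and 15/0.75 = 20, so it does the work of 20 v 20 unadjusted. The two-sided detectable d falls from 1.02 to 1.02 × √0.75 = 0.89.

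These are large-sample factors. Estimating the slope with 30 patients multiplies the ANCOVA variance by about 1 + 1/(30−4) = 27/26. At ρ = 0.5 that gives 0.75 × 27/26 = 0.78, a saving nearer 22%.

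**Adding the second rating.** With the mean of two ratings as covariate, the factor is 1 − 2ρ²/(1+r). At ρ = 0.5:
- r = 0.6: 1 − 0.5/1.6 = 0.688, and 0.688/0.75 = 0.917
- r = 0.7: 1 − 0.5/1.7 = 0.706, and 0.706/0.75 = 0.941
- r = 0.8: 1 − 0.5/1.8 = 0.722, and 0.722/0.75 = 0.963

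The second rating therefore removes a further 4-8%, equivalent to 0.6-1.4 patients per arm (15/0.963 − 15 to 15/0.917 − 15). Nearly all of the gain comes from adjusting at all.

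**Regression to the mean, as a conditional illustration only.** Suppose entry had required a screening score of at least 4, with SD 2 and source mean m. No such rule exists in the documents. The expected fall without any effect is (1−r) × 2 × φ(c)/(1−Φ(c)), where c = (4−m)/2. For m = 5, c = −0.5 and the ratio is 0.509, which gives 0.51 points at r = 0.5 and 0.20 at r = 0.8. Over m = 4-6 and r = 0.5-0.9 the range is 0.06-0.80 points.

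In simulation with no true effect (m = 5-6, r = 0.5-0.8), the two-sided 0.05 paired test showed significant improvement as follows (nominal 2.5%):
- From the screening rating: 7-29% of trials at n=30 and 5-17% at n=15.
- From the pre-graft rating: 2-3%.

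**The case against.** A reader might infer that the paired test is committed to the screening rating and so carries regression to the mean. Section 2.18 does not say that. Its wording fits the pre-graft rating at least as well, and the word baseline is used for the pre-graft visit too. Entry has no numeric cut-off on the pain form. The score of 4 in section 2.5.1 is context, and eligibility rests on patient and team report and on a persistent state: at least 3 months of failed fitting and, for socket users, at least 5 socket adjustments. Regression to the mean is therefore a risk, not a demonstrated feature. This part of the objection stands.

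A reader might also infer that the second rating is discarded. Nothing excludes it; the repeated measures ANOVA could include it. It would add little beyond single-rating ANCOVA in any case.

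It can be said that the plan never specifies change scores. That is true, but it does not remove the point. An unadjusted comparison is no better at ρ = 0.5, and with one pre and one post value the group-by-time test in a repeated measures ANOVA is the change-score test.

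Finally, averaging both ratings is not automatically safe. The trial is non-blinded (section 2.3). Section 2.5.1 describes randomization alongside screening without saying when the assignment is released. If release comes before the pre-graft visit, that rating may be affected by knowledge of the arm. This stands, and the fix is made conditional on it.

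**Conclusion.** The point holds as an available gain in precision together with an undefined baseline. Section 2.18 states no baseline adjustment for the between-arm pain comparison, although a suitable covariate is collected twice. At an assumed ρ of 0.5, ANCOVA on one rating cuts variance by about 25% against a change score or an unadjusted comparison (about 22% after the small-sample correction). The second rating adds 4-8% for r of 0.6-0.8.

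The plan also leaves the before value undefined, and the pain rating that it heads as baseline is the one more exposed to regression to the mean. That concerns the within-group test only. Its presence and size cannot be determined from the documents. It would be expected equally in both randomized arms, so it does not bias the contrast between them.

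**What to change.** In section 2.18:

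1. Compare post-operative pain between arms by ANCOVA at a named visit, or by a mixed model across visits, with pre-operative pain as covariate.
2. Define that covariate as the mean of the screening and pre-graft ratings if the pre-graft rating precedes release of the assignment, and as the screening rating alone otherwise. State in section 2.5.1 when the assignment is released.
3. In any before/after figure, take the pre-graft rating as the before value, and say that the change is descriptive and not an estimate of treatment effect. This removes the part of any fall that is due to selection on the screening score. It does not remove a fall that arises because patients present when their pain is unusually high.

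The cost is wording. Both ratings are already scheduled, no visit or form is added, and the fallback in step 2 avoids any change to the randomization procedure.
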